#### **4.4.2.3. Participant Discontinuation/Withdrawal of Consent**

Subjects may withdraw from the study at any time, for any reason, and may leave the study without specifying a reason at his/her own request. Additionally, subjects may request destruction of any samples taken and not tested, and the Investigator must document this in the site study records.

The Investigator should make all efforts to obtain information about possible underlying AEs leading to the decision to withdraw from study participation. Any AE or SAE information elicited must be documented in the subject's source documents and the eCRF. Refer to the SOA ([Appendix 1](#)) for data to be collected at the time of study discontinuation and follow-up and for any further evaluations that need to be completed.

Unless the subject who prematurely discontinues trial participation, specifically withdraws consent for any follow-up contact, all subjects will continue to be contacted at the same visit interval through the end of the study to obtain their health status. Investigators and site staff should encourage subjects to allow as much follow-up as possible and will need to clearly identify and document in writing as to which of the following options the subject has chosen.

- The subject has withdrawn from further treatment with study drug but will agree to continue with study visits and study assessments through the end of the Double-blind Treatment Period.
- The subject has withdrawn from further treatment with study drug, will not agree to continue with study visits and study assessments, but will agree to phone call assessments in accordance with the visit schedule.
- The subject is not willing to be contacted in accordance with the visit schedule but will allow the Investigator access to their medical records and EOS contact.

- The subject is not willing to allow any direct contact, access to medical records, or contact with care provider. In this case, public records may be used to confirm vital status at the end of the study.

For the purpose of this protocol, only subjects who are not willing to allow any direct contact, access to medical records, or contact with care provider will be deemed as subjects who have withdrawn consent.

If a subject decides to withdraw consent from study participation, it is necessary to ensure that relevant safeguards are put in place to maintain the individual's safety in the case of any future safety issues that are discovered. In this case, the decision to withdraw informed consent should be put in writing and, if possible, signed by the subject or subject's representative. A copy of this document should be maintained at the study site (with key data items recorded in the eCRF).

[figure not shown]
This written information should specify which aspect(s) of the study consent is being withdrawn as described above. In accordance with International Conference on Harmonisation (ICH) guidelines, FDA guidance, and other international ethical directives, data that have already been collected and incorporated into the study database, including the results of laboratory assays, will continue to be processed. In addition, every effort should be made to have the subject return to the clinic for the final EOT visit as described in the SOA ([Appendix 1](#)).

If the subject or the subject's representative refuses to withdraw consent in writing, the site must document and the Investigator must attest by signature, the reason for the subject's failure to withdraw the consent in writing. The Sponsor or designee should be immediately notified.

#### **4.4.2.4. Liver Injury**

Discontinuation of study treatment for abnormal liver tests should be considered by the Investigator when a subject meets one of the conditions outlined in the algorithm in [Figure 2](#) or if the Investigator believes that it is in the best interest of the subject. In all cases of suspected liver injury, a discussion with Sponsor or Sponsor designee is required prior to withdrawing the subject.

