**Figure 2. Suggested Liver Injury Stopping Criteria**

Suggested actions and follow-up assessments can be found in [Appendix 7](#).

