## APPENDIX 7. LIVER SAFETY SUGGESTED ACTIONS AND FOLLOW-UP ASSESSMENTS

Phase 2 liver function stopping criteria are designed to ensure subject safety and to evaluate liver event etiology.

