### Phase 2 Liver Function Stopping Criteria and Follow-up Assessments

Liver Function Stopping Criteria	
ALT-absolute	ALT $\geq 5 \times$ ULN
ALT Increase	ALT $\geq 3 \times$ ULN persists for $\geq 4$ weeks
Bilirubin	ALT $\geq 3 \times$ ULN and bilirubin $\geq 2 \times$ ULN ( $>35\%$ direct bilirubin)
INR^2	ALT $\geq 3 \times$ ULN and international normalized ratio (INR) $>1.5$ , if INR measured
Cannot Monitor	ALT $\geq 3 \times$ ULN and cannot be monitored weekly for 4 weeks
Symptomatic	ALT $\geq 3 \times$ ULN associated with symptoms (new or worsening) believed to be related to liver injury or hypersensitivity

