### Actions and Follow-up Assessments following ANY Liver Function Event that Requires Study Treatment Discontinuation

Actions	Follow-up Assessments

• Immediately discontinue study treatment.

• Report the event to the Sponsor within 24 hours.

• Complete the liver event eCRF and complete an SAE data collection tool if the event also met the criteria for an SAE.

• Perform liver function follow-up assessments.

• Monitor the subject until liver function test abnormalities resolve, stabilize, or return to Baseline (see MONITORING).

• Do not restart/rechallenge subject with study treatment unless allowed per protocol and Sponsor Medical Governance approval is granted.

• If restart/rechallenge not granted, permanently discontinue study treatment and may continue subject in the study for any protocol specified follow up assessments.

	

• Viral hepatitis serology.

• Blood sample for PK analysis obtained after the most recent dose.

• Serum creatine phosphokinase and lactate dehydrogenase.

• Fractionate bilirubin if total bilirubin is <math>\geq 2 \times</math>ULN.

• Complete blood count with differential to assess eosinophilia.

• Record the appearance or worsening of clinical symptoms of liver injury, or hypersensitivity, on the AE report form.

• Record use of concomitant medications (including acetaminophen, herbal remedies, and other over-the-counter medications) on the concomitant medications report form.

• Record alcohol use on the liver event alcohol intake eCRF.

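### Section 4.4.2.4 asks the Investigator only to consider stopping study drug on liver criteria, the working text of Appendix 7 directs stopping, and no visible text says which governs

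*Combined protocol and SAP*

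**What the plan says.** Section 4.4.2.4 of the protocol sets the rule for liver injury in permissive terms: "Discontinuation of study treatment for abnormal liver tests should be considered by the Investigator when a subject meets one of the conditions" shown in Figure 2. It adds that in suspected liver injury "a discussion with Sponsor or Sponsor designee is required prior to withdrawing the subject". The figure is titled "Suggested Liver Injury Stopping Criteria", and the line under it reads "Suggested actions and follow-up assessments can be found in" Appendix 7. The appendix title repeats the label: "LIVER SAFETY SUGGESTED ACTIONS AND FOLLOW-UP ASSESSMENTS".

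Inside Appendix 7 the tone changes. Its opening sentence is "Phase 2 liver function stopping criteria are designed to ensure subject safety and to evaluate liver event etiology". The table headed "Phase 2 Liver Function Stopping Criteria and Follow-up Assessments" lists six stopping criteria. The next table is headed "Actions and Follow-up Assessments following ANY Liver Function Event that Requires Study Treatment Discontinuation". Its first action is to discontinue study treatment immediately, and it bars restart or rechallenge unless the protocol allows it and the Sponsor's Medical Governance approves. Footnote 1 directs discontinuation on ALT at or above 3×ULN with bilirubin at or above 2×ULN when bilirubin cannot be fractionated straight away. Continued dosing is permitted only in a separate increased-monitoring tier at the end of the appendix. That tier sends the subject back to the stopping actions as soon as a stopping criterion is met.

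**The concern.** An Investigator who opens Section 4.4.2.4 learns that stopping is a matter to weigh. One who opens Appendix 7 is told to stop. With about 20 US sites, two of them could each follow the protocol as written and yet handle the same liver result differently, one stopping study drug and one giving the next dose.

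The hepatic risk makes this more than a matter of style. Section 1.3 lists AST and/or ALT elevation as the only important identified risk, and Table 1 traces it to five named clinical studies as well as nonclinical work. Footnote 2 of Appendix 7 treats the bilirubin and INR combinations as possible Hy's Law. What is at stake is subject safety and uniform handling across sites.

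**Working it through.** There is no planned figure to reproduce. The check compares the texts and then counts the doses that the difference could touch.

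**1. The texts side by side**

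| Place | Wording | Force |
|---|---|---|
| Section 4.4.2.4 | stopping is to be considered | permissive |
| Figure 2 title; sentence under it; Appendix 7 title | suggested | permissive label |
| Appendix 7, criteria table | six stopping criteria | directive label |
| Appendix 7, actions table | discontinue immediately; no restart without approval | directive |
| Appendix 7, footnote 1 | discontinue on laboratory values alone | directive |
| Appendix 7, monitoring tier | may continue, until a stopping criterion is met | limited permission |

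**2. Does Appendix 7 have a stop-or-continue structure?** The monitoring tier starts at ALT of 3×ULN and has four limiting entry conditions. Each faces one of the six stopping rows:

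- ALT below 5×ULN against ALT at or above 5×ULN: exact reverse.
- Weekly monitoring possible against not possible: exact reverse.
- Bilirubin below 2×ULN against bilirubin at or above 2×ULN: reverse, except that the stopping row also needs a direct fraction above 35%.
- No liver-related symptoms against such symptoms: reverse only in part, because the stopping row is limited to new or worsening symptoms.

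The other two rows (ALT at or above 3×ULN for 4 weeks or more; INR above 1.5) are reached through the clause that ends the tier. The structure is therefore largely complementary. An express permission to continue would hardly be needed if continuing were always at the Investigator's discretion.

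Two cases fall in neither tier when no other criterion is met, both with ALT at or above 3 and below 5×ULN: bilirubin at or above 2×ULN with a measured direct fraction of 35% or less; and stable, pre-existing symptoms attributed to the liver.

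**3. Does other visible text settle it?** No precedence statement appears. Section 4.4.2.1 says only that drug may be halted for a serious event.

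**4. Doses that remain.** Section 5 gives doses at Weeks 0, 2, 6, 10, 14, 18, 22, 26 and 30, so 9 in all. After dose k, 9 − k remain:

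- Criterion met after Day 1 and before Week 2 (an unscheduled test): 9 − 1 = 8.
- Scheduled Week 2 sample, result after that day's dose: 9 − 2 = 7.
- Weeks 6, 10, 14, 18, 22, 26 likewise: 6, 5, 4, 3, 2, 1.
- After the Week 30 dose, or at Week 34: 0.

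**5. What a mandatory stop means for restart.** Section 4.4.2.2 withdraws a subject from study drug once more than one dose is missed. Take a last dose at Week w, with w from 2 to 22. The missed doses are w + 4 and w + 8, so restart must come by w + 8. A stop just after the dose leaves 8 weeks for approval; a stop just before the next dose leaves 4. After the Day 1 dose the second missed dose is Week 6, so the limit is at most 6 weeks. After the Week 26 dose only one dose is left and the limit cannot be reached. This assumes no earlier missed dose and ignores the ±3-day windows.

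**The case against.** The strongest reply is that everything is advisory. The body text, the figure title, the cross-reference and the appendix title all point that way, and the heading of the actions table can be read as applying once stopping has been judged necessary. Discretion may also be deliberate: the neighbouring sections on QTcF (4.4.2.5) and pregnancy (4.4.2.6) say firmly that the subject will be withdrawn, and the liver section does not. Section 4.4.2.4 attaches its wording to Figure 2, which cannot be seen here and may itself separate stopping from monitoring.

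That reading is possible, so a flat contradiction is not proved. It does not remove the problem. Under it, nothing visible requires stopping drug for possible Hy's Law, on the one important identified risk, while QTcF and pregnancy have firm rules. Nor would a directive Figure 2 change the permissive sentence that introduces it.

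It is also fair that a site which kept dosing would have to set aside several plain instructions in Appendix 7, and would do so under observation. Possible Hy's Law must be reported as an SAE, the Sponsor hears within 24 hours, chemistry is drawn at each dosing visit, and the DMC reviews unblinded safety data. These steps make prolonged divergence less likely, but none of them requires a stop.

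Table 1 lends little support either way. It names no stopping rule for AST/ALT elevation, but it names none for any other risk.

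**Conclusion.** The concern stands as a conflict of wording on a safety rule that should be resolved. It rests on the visible text only; what Figure 2 says is unknown.

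The size is limited. The documents give no rate of qualifying liver events, so no frequency is estimated. Between 0 and 8 of 9 doses remain when a criterion is met, depending on timing. The upper figures are ceilings that require every later chance to stop to be passed, not expected exposure. In Cohort A's placebo arm the remaining doses contain no namilumab.

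A reader might infer three stronger things that the documents do not support:

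- That the required Sponsor discussion contradicts an immediate stop. It precedes withdrawing the subject, which is not the same act as stopping drug.
- That the primary endpoint is distorted, because it includes AEs leading to discontinuation. Nothing in the documents allows such an effect to be sized, and none is claimed.
- That the two tiers of Appendix 7 are perfect opposites, so the binding reading is certain. Only two of the four facing pairs match exactly.

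**What to change.** Replace the text of Section 4.4.2.4 with:

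> Study drug must be stopped immediately when a subject meets any liver stopping criterion in Appendix 7, and the Sponsor notified within 24 hours. The Investigator may also stop study drug at any time if that is best for the subject. Sponsor discussion is required before withdrawing the subject from the study, not before stopping study drug. Restart or rechallenge is not permitted unless the protocol allows it and Sponsor Medical Governance has approved it (Appendix 7), and it is subject to the missed-dose limit in Section 4.4.2.2.

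Delete the word *suggested* from the Figure 2 title, the sentence under it, the Appendix 7 title, the table of contents and the list of figures. Check Figure 2 against Appendix 7 and align it if they differ.

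Optionally, assign the two cases that fall in neither tier to stopping or to monitoring, as the sponsor's clinicians decide.

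The core change is six wording edits (the section and five labels) plus one check of the figure, carried by a protocol amendment and a notice to sites. It adds no tests or visits to those already listed. The optional cases need further edits to the Appendix 7 tables, and the work on Figure 2 cannot be sized without seeing it.

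The downside is less Investigator discretion. Some rises with another cause will also stop drug, permanently if approval takes long enough for more than one dose to be missed.

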**Figure 2. Suggested Liver Injury Stopping Criteria**

Suggested actions and follow-up assessments can be found in [Appendix 7](#).

#### 4.4.2.5. Cardiac Changes

If a clinically significant finding is identified (including, but not limited to changes from baseline in QTcF after enrollment), the Investigator or qualified designee will determine if the subject can continue in the study and if any change in subject management is needed. This review of the ECG printed at the time of collection must be documented. Any new clinically relevant finding should be reported as an AE.

A subject who meets the following criterion based on the average of triplicate ECG readings will be withdrawn from the study.

- QTcF >500 msec OR uncorrected QT >600 msec.

For subjects with underlying bundle branch block, follow the discontinuation criteria listed in [Table 2](#).

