### **3.1.2. 34-week Treatment Period**

All subjects will begin the 34-week Treatment Period after confirmation that all protocol eligibility criteria have been met. The Treatment Period includes up to 11 clinic visits and 16 phone or telemed visits as described in the Schedule of Assessments (SOA; [Appendix 1](#)).

Subjects in Cohort A will begin tapering their OCS at the time of randomization as described in Appendix 8. During the steroid taper period, Investigators will contact subjects weekly via phone or telemed visits as outlined in [Appendix 1](#).

If a subject needs to discontinue study drug (temporarily or permanently) or terminate study participation before completion of the Treatment Period, please refer to [Section 4.4.2](#) for detailed instructions regarding recommended follow-up.

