#### **4.4.2.2. Temporary Cessation of Study Drug**

Study drug may temporarily be stopped for safety reasons at the discretion of the Investigator; however, not more than one dose may be missed. If more than one dose is missed, the subject will be withdrawn from study drug and followed for safety.

If the Investigator unblinds subject data for safety purposes, study drug will be permanently withdrawn.

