**Table 2. Discontinuation Criteria for Subjects with Underlying Bundle Branch Block**

Baseline QTcF with Bundle Branch Block	Discontinuation QTcF Threshold with Bundle Branch Block
<450 msec	>500 msec
450 to 500 msec	≥530 msec

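### The QT stopping rule in Section 4.4.2.5 removes the subject from the study, not just from study drug; read literally, scheduled cardiac assessments then stop after one early termination visit

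*Combined protocol and SAP*

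**What the plan says.** Section 4.4.2.5 (Cardiac Changes) belongs to Section 4.4.2, which is headed as dealing with discontinuation of study treatment. Its mandatory action is different: "A subject who meets the following criterion based on the average of triplicate ECG readings will be withdrawn from the study". The criterion is QTcF above 500 msec or uncorrected QT above 600 msec. For bundle branch block the section says "For subjects with underlying bundle branch block, follow the discontinuation criteria listed in" Table 2, whose column is titled "Discontinuation QTcF Threshold with Bundle Branch Block". Neither the sentence nor the table says what is being discontinued.

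Other stopping rules act on the drug. After more than one missed dose, "the subject will be withdrawn from study drug and followed for safety" (Section 4.4.2.2). For liver events without approved rechallenge, Appendix 7 tells the site to "permanently discontinue study treatment and may continue subject in the study for any protocol specified follow up assessments".

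Two rules are closer to the QT rule. A confirmed pregnancy also ends study participation (Section 4.4.2.6), and a needed dose reduction leads to stopping drug and completing the end-of-treatment assessments (Section 5.3.1).

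Footnote b of the Schedule of Assessments (Appendix 1) gives anyone withdrawn early one set of Week 34 procedures, where possible. Section 4.4.4 bars re-entry and lets the sponsor replace the subject.

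**The concern.** The subjects affected would be chosen by an ECG result, and change in ECG parameters and cumulative arrhythmia burden are both secondary endpoints (Section 2.2). Data lost this way are not lost at random with respect to those endpoints. Section 8.4 rules out imputation. It promises a sensitivity analysis, which can explore the bias but cannot recover the values.

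There is also a safety cost. After the early termination visit, no scheduled ECG shows whether the interval recovers off drug. The strongest relatedness category in Appendix 3 looks for exactly that: an event that abates once drug is stopped.

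Finally, the text supports two readings, so sites could handle the same ECG differently.

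**Working it through.** **Inputs.** All come from the Schedule of Assessments (Appendix 1) and Sections 7.1.1.2 and 7.1.2.1. The protocol gives no figure of its own to reproduce.
- 12-lead ECG after Baseline: Weeks 2, 6, 10, 14, 18, 22, 26, 30, 34.
- Echocardiogram after Screening: Weeks 10, 22, 34.
- PET/CT after Screening: Weeks 22 and 34 (Cohort A); Weeks 10 and 34 (Cohort B).
- ePatch on treatment: Baseline and Weeks 2, 6, 10, 14, 18, 22, 26, 30. That is 9 placements × 10 days = 90 days. None is scheduled at Week 34 or at early termination.

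**Formula for visits and scans.** Net loss = assessments scheduled after the trigger visit through Week 34, minus the one done at the early termination visit. Assessments due at the trigger visit itself are taken as done.

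| Trigger | ECG visits | Echo | PET/CT, Cohort A | PET/CT, Cohort B |
|---|---|---|---|---|
| Week 2 | 8 − 1 = 7 | 3 − 1 = 2 | 2 − 1 = 1 | 2 − 1 = 1 |
| Week 10 | 6 − 1 = 5 | 2 − 1 = 1 | 2 − 1 = 1 | 1 − 1 = 0 |
| Week 22 | 3 − 1 = 2 | 1 − 1 = 0 | 1 − 1 = 0 | 1 − 1 = 0 |
| Week 30 | 1 − 1 = 0 | 1 − 1 = 0 | 1 − 1 = 0 | 1 − 1 = 0 |

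If the early termination visit does not take place, the first number in each cell is the loss.

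**ePatch days lost.** The lower figure assumes a patch is still placed at the trigger visit, the upper that it is not.
- Week 2: 7 × 10 = 70 to 8 × 10 = 80
- Week 10: 5 × 10 = 50 to 6 × 10 = 60
- Week 22: 2 × 10 = 20 to 3 × 10 = 30
- Week 30: 0 to 1 × 10 = 10

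**Share of a Cohort A arm.** 10 subjects × 90 days = 900 planned patch-days. One Week 2 case removes 70/900 = 7.8% to 80/900 = 8.9% of them.

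**Timing.** These are counts only. For any trigger before Week 34, the early termination values come earlier than Week 34, which Section 2.2 makes the primary assessment for mean change from baseline. Equal counts therefore do not mean equal information.

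**Lower bound.** If the site keeps the subject on the visit schedule, every entry above is zero.

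**The case against.** The best reply is that the protocol already provides for continued visits. Section 3.1.2 sends a subject who must "discontinue study drug (temporarily or permanently) or terminate study participation before completion of the Treatment Period" to Section 4.4.2, so both kinds of stop go to the same place. Within it, Section 4.4.2.3 addresses subjects who leave the trial prematurely: unless they refuse follow-up, "all subjects will continue to be contacted at the same visit interval through the end of the study to obtain their health status". One listed option is a subject off drug who "will agree to continue with study visits and study assessments through the end of the Double-blind Treatment Period".

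This stands as a possible reading, and it is why the lower bound is zero. It does not settle the matter. The universal requirement is contact about health status, not testing. The continue-visits option is worded for a subject who has stopped study drug and agrees to stay, not for one whom the protocol requires to be withdrawn from the study. It runs to the end of a double-blind period that open-label Cohort B does not have, and Section 4.4.2.5 does not point to it.

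Four stronger inferences are tempting, and the documents do not support them.
- *The QT rule is the only exception to a keep-all-visits policy.* No such policy exists. The missed-dose rule promises only safety follow-up, the liver rule is permissive, and the pregnancy and dose-reduction rules lead to similar exits.
- *Follow-up ends, or the safety event is lost.* A new clinically relevant finding is reported as an adverse event. Events that led to stopping drug are followed (Section 7.3.1), for 56 days or until resolution or stabilization (Appendix 3). Unscheduled visits are available, and the subject stays in the Safety Population. Recovery ECGs may well be obtained; they are just not scheduled.
- *ePatch monitoring ends at the early termination visit.* None is scheduled there, so it ends before.
- *Every case costs a Week 34 value.* The early termination visit consists of the Week 34 procedures, and a trigger at Week 34 costs nothing. What changes is the timing.

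The affected cardiac endpoints are also secondary, and the study plans no hypothesis tests and makes no power claim.

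**Conclusion.** The point holds as an ambiguity with a real cost under its literal reading. Section 4.4.2.5 mandates study withdrawal where stopping drug would protect the subject equally well. Table 2 leaves the action unstated, and nothing requires scheduled cardiac tests after the early termination visit.

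Per case, the loss ranges from zero (softer reading) to 7 ECG visits, 2 echocardiograms, 1 PET/CT and 70 to 80 of 90 ePatch days for a Week 2 trigger. It falls to at most 10 ePatch days at Week 30. The upper figures assume the literal reading and a completed early termination visit.

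The documents do not show how often the limit will be crossed, so no total loss for the trial can be given. Entry allows a screening QTcF up to 480 msec without bundle branch block, 500 − 480 = 20 msec below the limit, but that margin is not a frequency. With 10 subjects per Cohort A arm, a single early case would be visible in the arrhythmia summary. The change is worth making because it is cheap and removes a loss tied to the outcome being measured.

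**What to change.** Keep every QT limit and every Table 2 threshold. Replace the action in Section 4.4.2.5, and state that it also applies to Table 2, with:

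*will permanently discontinue study drug and will be asked to continue scheduled visits and assessments through Week 34, with the follow-up options in Section 4.4.2.3 if the subject declines; the ET visit is done only if the subject leaves the scheduled visits.*

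This is a wording amendment. It adds no new type of assessment and no PET/CT beyond the planned three. The downside is that visits continue for a subject off drug, and later data mix on-drug and off-drug time.

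Three additions are optional: a sentence in Section 4.4.4 that these subjects are not replaced, an off-drug flag in the SAP, and a SAP listing of each case with its trigger and follow-up ECGs. The main change does not depend on them.
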